5.3 Pre-Medications

None required. Anti-emetics may be administered per clinical discretion.

5.4 Permitted concomitant therapy

Medications required to treat adverse events, manage cancer symptoms or concurrent stable disease (e.g., controlled hypertension), or manage pain are permitted.

Supportive care agents, including erythropoietin, granulocyte growth factors, or blood transfusions are permitted only after patients have developed grade 3 or higher anemia or neutropenia.

Corticosteroids for the treatment of conditions other than CLL/SLL are permitted at maximum doses of prednisone 20mg daily (or steroid equivalent) are permitted, and at a stable does (ie. no higher than 20mg for at least 28 days prior to initiation of DMF).

The patient needs to notify the investigational site about any new medications he/she takes after the start of the study medication. All medications (other than study drug) and significant non-drug therapies (including physical therapy and blood transfusions) administered after the patient starts treatment with study drug must be listed on the CRF.

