5.2 Definition of Dose-Limiting Toxicity

Dose Limiting Toxicity (DLT) is defined as any of the following adverse events that are considered by the investigator to be possibly, probably or definitely related to DMF within the DLT evaluation timeframe.

- Non-hematologic adverse events: grade 3 (CTCAE 4) or higher, lasting more than 7 days despite appropriate medical management.
- Hematologic adverse events: grade 3 (iwCLL 2008) or higher, lasting more than 7 days despite appropriate medical management, with the exception of: any grade lymphopenia ; or any grade lymphocytosis.
- Grade 4 non-hematologic (CTCAE 4) of any duration
- Grade 4 hematologic (iwCLL 2008) of any duration.
- Any clinically significant toxicity that precludes administration of the next scheduled dose beyond 14 days

Replacement patients may be enrolled for patients who withdraw from investigational treatment for a reason that is definitely unrelated to toxicity of the study agent or disease progression (e.g. patient preference, loss to follow-up). Replacement patients will ensure enough patients are enrolled to evaluate the primary endpoint.

The DLT evaluation timeframe is from the first dose of DMF until day 56 of the trial.

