5.7 Toxicities and Dosing Delays/Dose Modifications

Any patient who receives treatment on this protocol will be evaluable for toxicity. Each patient will be assessed for the development of toxicity according to the NCI Common Toxicity Criteria for Adverse Events (CTCAE), version 4.03 for non-hematologic adverse events, and 2008 international working group criteria (iwCLL, Hallek et al, appendix B) for hematologic adverse events. Dose adjustments should be made according to the system showing the greatest degree of toxicity. Patients are assessed for safety and tolerability on Day 8, Day 28, and Day 42 after starting DMF.

Toxicity – NCI CTCAE Grade (Hematologic- iwCLL)	Occurrence	Dose Modification
Non-hematologic		
Grade ≥ 3	1st	Withhold study treatment until resolved to Grade ≤ 1.

		Resume study treatment at the next lower dose level.
	Repeat	Discontinue therapy.
Hematologic*		
Grade \geq 3	1st	Withhold study treatment until resolved to ANC \geq 1000/mm ³ , hemoglobin is \geq 8 gm/dL, and platelet count \geq 50,000/mm ³ . Resume study treatment at same dose.
	2nd	Withhold study treatment until resolved to ANC \geq 1000/mm ³ , hemoglobin is \geq 8 gm/dL, and platelet count \geq 50,000/mm ³ . Resume study treatment at the next lower dose level.
	3rd	Permanently discontinue study treatment.
*Dose adjustments or dose holds for hematologic toxicity will apply even if the baseline values are lower than these thresholds due to heavily infiltrated marrow. In those cases, growth factors and/or blood product transfusion may be administered prior to continuing with DMF.		

Notes:

1. If any of the above are noted, the patient will be re-assessed within 7 days by the treating physician or investigator. Isolated laboratory abnormalities may be re-evaluated by laboratory draw only, or based on physician or investigator discretion.
2. DMF can be delayed for a maximum of 14 days; if not restarted in that time-span, study treatment will be permanently discontinued.
3. If dose is decreased for toxicity, dose re-escalation is not planned.
4. For invasive procedures, not including biopsies or venous catheter placement: withhold study treatment for 1 week prior to procedure, and at least 1 week following surgery until satisfactory wound healing has been achieved.

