7.2 Safety/tolerability

Analyses will be performed for all patients having received at least one dose of study drug. The study will use the CTCAE version 4.03 (<http://ctep.cancer.gov/reporting/ctc.html>) for reporting of non-hematologic adverse events and modified iwCLL criteria for hematologic adverse events (Appendix B).

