8.2 Severity

Hematologic adverse events will be graded using a modified iwCLL criteria (appendix 2).

All non-hematologic adverse events will be graded according to the NCI Common Terminology Criteria for Adverse Events (CTCAE) version 4.03. The CTCAE v4.03 is available at <http://ctep.cancer.gov/reporting/ctc.html>

If no CTCAE grading is available, the severity of an AE is graded as follows:

Mild (grade 1): the event causes discomfort without disruption of normal daily activities.

Moderate (grade 2): the event causes discomfort that affects normal daily activities.

Severe (grade 3): the event makes the patient unable to perform normal daily activities or significantly affects his/her clinical status.

Life-threatening (grade 4): the patient was at risk of death at the time of the event.

Fatal (grade 5): the event caused death.

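### Section 5.4 omits thrombocytopenia from its triggers for supportive care, so isolated Grade 3-4 thrombocytopenia gives no stated permission for platelet transfusion

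*Combined protocol and SAP*

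**What the plan says.** Section 5.4 places erythropoietin, granulocyte growth factors and transfusion under one restriction: "blood transfusions are permitted only after patients have developed grade 3 or higher anemia or neutropenia". It names no grading scale. Its opening sentence permits medications for adverse events, but its last paragraph, on CRF recording, lists transfusion among "significant non-drug therapies (including physical therapy and blood transfusions").

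Elsewhere hematologic events are graded by iwCLL: the 5.7 table is headed "Hematologic- iwCLL", 7.2 refers to "modified iwCLL criteria for hematologic adverse events (Appendix B"), and 8.2 states that "Hematologic adverse events will be graded using a modified iwCLL criteria". In Appendix B, Grade 3 for hemoglobin (Hb) or platelets is a 50%-74% fall from the pretreatment value and Grade 4 is a fall of 75% or more. A platelet count below 20,000/µL is Grade 4 at any percentage fall, except where the pretreatment count was already that low.

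Under 5.2, related hematologic events are DLTs if "grade 3 (iwCLL 2008) or higher, lasting more than 7 days despite appropriate medical management", or at Grade 4 for any duration. Inclusion 12 requires platelets of at least 50,000/µL, Hb of at least 8.0 g/dL (erythropoietin support accepted) and ANC above 1000/µL. Inclusion 10 lists progressive thrombocytopenia, at 100,000/µL or lower, as one of eight alternative indications for treatment.

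**The concern.** The restriction is worded as a limit, not as an example, and it leaves out one of the three cytopenias that the protocol grades and manages. Section 5.7 withholds DMF for Grade 3 or higher hematologic toxicity until, among other counts, platelets recover to 50,000. Section 5.2 tests whether a Grade 3 event persists under management. Section 5.4 then gives no permission for the ordinary management of a low platelet count.

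This matters because 11.5 requires strict adherence outside emergencies, and 11.5.2 requires prior approval by the Principal Investigator and the IRB for other planned departures. A routine platelet transfusion should not need either route. The restriction applies whether the fall comes from DMF or from the CLL itself.

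A smaller point lies in the same sentence. Inclusion 12b admits patients on erythropoietin, but 5.4 opens erythropoietin only after Grade 3. For corticosteroids 5.4 does deal with stable prior use ("no higher than 20mg for at least 28 days prior to initiation of DMF"); for erythropoietin it does not.

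**Working it through.** **Inputs.** Trigger: 5.4. Grade bands and the 20,000 floor: Appendix B. Entry limits: inclusion 12. Entry indications: inclusion 10. The values are assumed to be below the laboratory's normal range, as Appendix B requires for grading.

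**Platelets.** With pretreatment count B, Grade 3 starts at 0.5 × B. Grade 4 starts at 0.25 × B or below 20,000, whichever is met first on the way down. The floor governs for B below 80,000, because 0.25 × 80,000 = 20,000.

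| Pretreatment (/µL) | Grade 3 starts at | Grade 4 starts at | Opens 5.4 on its own? |
|---|---|---|---|
| 50,000 | 25,000 | below 20,000 | No |
| 60,000 | 30,000 | below 20,000 | No |
| 75,000 | 37,500 | below 20,000 | No |
| 100,000 | 50,000 | 25,000 | No |

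Two examples:
- 60,000 to 15,000: 1 − 15/60 = 75%, Grade 4.
- 55,000 to 19,000: 1 − 19/55 = 65.5%, in the Grade 3 band by percentage but Grade 4 by the floor.

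Neither opens 5.4 unless Grade 3 anemia or neutropenia is also present. This does not depend on the grading scale, since thrombocytopenia is missing from the list at every grade.

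**Whether other text supplies the permission.**
- The 5.7 footnote says "growth factors and/or blood product transfusion may be administered prior to continuing with DMF", but only where baseline values are below ANC 1000, Hb 8 or platelets 50,000. Inclusion 12 largely excludes those patients, and 5.4 does not refer to the footnote.
- Section 5.2 assumes management but does not authorise any.
- The opening sentence of 5.4 is general and concerns medications. The restriction is the specific rule and would do little if the general sentence overrode it.

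**Whether the added trigger could hide a Grade 3 event.** Permission would open only once the count is at or below 0.5 × B, so Grade 3 has already been reached and recorded. Onset cannot be hidden. What happens afterwards can change: the event may end within 7 days or stop short of Grade 4.

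**Anemia, for information.** If 5.4 is read on iwCLL, the trigger is 0.5 × baseline Hb: 8 gives 4.0, 9 gives 4.5, 10 gives 5.0 and 11 gives 5.5 g/dL. Hb 7.0 from 8.0 is a 12.5% fall (Grade 1), and 6.0 from 10 is 40% (Grade 2). A transfusion threshold of Hb below 8 would come before Grade 3 for every baseline under 16 g/dL, because 0.5 × 16 = 8.

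**The case against.** The best case for leaving the text alone has three parts.

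First, the protocol shows no wish to deny platelets. Section 5.5 does not prohibit transfusion, 5.2 takes management for granted, and the 5.7 footnote allows blood products in some patients. The listing of transfusion as a non-drug therapy sits in a recording instruction, while the restriction itself groups it with supportive care agents. That is fair as evidence of intent, and the omission is probably an oversight. It does not supply the permission.

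Second, harm is limited. Section 9.1 lists lymphocytopenia and transient eosinophilia, not thrombocytopenia, among DMF's effects. Treatment lasts 56 days and can be stopped, and progressive thrombocytopenia is only one of eight entry indications. A reader might infer that a bleeding patient would be refused platelets; the emergency exceptions in 11.5 and 11.5.1 answer that. All of this stands and keeps the point small.

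Third, withholding support until Grade 3 is a defensible choice in a 3+3 design driven by DLTs. This also stands. A reader might infer from the 4.0-5.5 g/dL figures that the anemia trigger is itself an error and that transfusion should be allowed at an absolute Hb. The documents do not support going that far: 5.4 names no scale, so the figures rest on reading iwCLL into it, and earlier transfusion could prevent a Grade 3 event from ever being seen.

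On erythropoietin, the restriction can be read as covering only support started on study. That makes it a matter for clarification, not a contradiction.

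**Conclusion.** The point holds for platelets. As written, 5.4 gives no permission for platelet transfusion in isolated Grade 3-4 thrombocytopenia, and nothing else in the protocol clearly gives it to patients who meet inclusion 12. For entry counts of 50,000 to 100,000/µL, that covers falls to 25,000-50,000 and below. This is a minor patient-safety wording correction. The documents give no frequency for such falls, so no likelihood can be stated.

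A reader might infer that the DLT rate or the MTD is biased by the present wording. That is not claimed: nothing in the documents shows that DLTs are miscounted because platelet support is missing from 5.4.

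The anemia threshold on iwCLL grading is something the sponsor's clinicians should note. Permitting transfusion before Grade 3 is a clinical trade-off with DLT detection and is not part of this correction.

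**What to change.** Amend 5.4 as follows:
- Add thrombocytopenia to anemia and neutropenia as a Grade 3 or higher trigger, and name iwCLL (Appendix B) as the scale.
- Require a platelet count before each platelet transfusion and grade on that count. Appendix B already requires pre-transfusion determinations for Hb.
- State that erythropoietin in use at entry under inclusion 12b may continue at a stable dose. Appendix B already treats its use as irrelevant to grading but to be documented.

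When response is assessed under 7.1, do not credit transfused platelet counts. The hemoglobin criteria there are restricted to untransfused values, but the platelet criteria are not.

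**Cost.** No new visits are needed, and transfusions must already be listed on the CRF. The real downside is that platelet transfusion after Grade 3 onset may shorten an event to 7 days or less, or stop it reaching Grade 4, so that it no longer meets those DLT criteria. Section 5.4 already accepts the same effect for anemia. Grading on the pre-transfusion count limits this but does not remove it.

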5.5 Prohibited concomitant therapy

Other investigational therapies must not be used while the patient is on the study. Anticancer therapy (chemotherapy, biologic or radiation therapy, and surgery) other than the study treatments must not be given to patients while the patient is on the study medication. If such agents are required for a patient then the patient must be discontinued from the treatment portion of the study.

5.6 Other Modalities or Procedures

Not applicable.

5.7 Toxicities and Dosing Delays/Dose Modifications

Any patient who receives treatment on this protocol will be evaluable for toxicity. Each patient will be assessed for the development of toxicity according to the NCI Common Toxicity Criteria for Adverse Events (CTCAE), version 4.03 for non-hematologic adverse events, and 2008 international working group criteria (iwCLL, Hallek et al, appendix B) for hematologic adverse events. Dose adjustments should be made according to the system showing the greatest degree of toxicity. Patients are assessed for safety and tolerability on Day 8, Day 28, and Day 42 after starting DMF.

Toxicity – NCI CTCAE Grade (Hematologic- iwCLL)	Occurrence	Dose Modification
Non-hematologic		
Grade ≥ 3	1st	Withhold study treatment until resolved to Grade ≤ 1.

		Resume study treatment at the next lower dose level.
	Repeat	Discontinue therapy.
Hematologic*		
Grade \geq 3	1st	Withhold study treatment until resolved to ANC \geq 1000/mm ³ , hemoglobin is \geq 8 gm/dL, and platelet count \geq 50,000/mm ³ . Resume study treatment at same dose.
	2nd	Withhold study treatment until resolved to ANC \geq 1000/mm ³ , hemoglobin is \geq 8 gm/dL, and platelet count \geq 50,000/mm ³ . Resume study treatment at the next lower dose level.
	3rd	Permanently discontinue study treatment.
*Dose adjustments or dose holds for hematologic toxicity will apply even if the baseline values are lower than these thresholds due to heavily infiltrated marrow. In those cases, growth factors and/or blood product transfusion may be administered prior to continuing with DMF.		

Notes:

1. If any of the above are noted, the patient will be re-assessed within 7 days by the treating physician or investigator. Isolated laboratory abnormalities may be re-evaluated by laboratory draw only, or based on physician or investigator discretion.
2. DMF can be delayed for a maximum of 14 days; if not restarted in that time-span, study treatment will be permanently discontinued.
3. If dose is decreased for toxicity, dose re-escalation is not planned.
4. For invasive procedures, not including biopsies or venous catheter placement: withhold study treatment for 1 week prior to procedure, and at least 1 week following surgery until satisfactory wound healing has been achieved.

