5.0 TREATMENT PLAN

5.1 Treatment Dosage and Administration

For Dose Level 1, DMF (Tecfidera formulation) will be administered at a dose of 120 mg PO BID (approximately 12 hours apart) for 2 x 28 day cycles.

For Dose Level 2, DMF will be administered at the currently used dose for patients with multiple sclerosis: 120 mg PO BID for 1 week, then escalate to the dose of 240mg PO BID for the remainder of 2 x 28 day cycles. The 1 week lead-in at 120 mg is to assist in toleration and initial side effects and is as per the standard prescribing information.

For Dose Level 3, DMF will be administered at the currently used dose for patients with multiple sclerosis: 120 mg PO BID for 1 week, then escalate to the dose of 360mg PO BID for the remainder of 2 x 28 day cycles.

The medication can be taken with or without food. Capsules should not be crushed or chewed. Capsules will be self-administered on an outpatient basis. On days in which patients are scheduled for assessment, capsules will be taken in clinic. Missed or vomited doses will be skipped. Patients are assessed for safety and tolerability on Day 8, Day 1 of each subsequent cycle, and 28 days and 56 days following the last dose of DMF.

Dose Level	DMF dose (all cohorts start at 120 mg PO BID dose for 1 week, then increase to the assigned dose)
1	120 mg PO BID
2	240 mg PO BID
3	360 mg PO BID

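### The dose-reduction rule in 5.7 has nowhere to go below 120 mg BID, and on one reading it takes a Level 3 patient with a lead-in event up to 240 mg BID

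*Combined protocol and SAP*

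**What the plan says.** The table in section 5.7 (Toxicities and Dosing Delays/Dose Modifications) has treatment withheld for toxicity of Grade 3 or higher. For a first non-hematologic event, and for a second hematologic event, the action on recovery is "Resume study treatment at the next lower dose level". A first hematologic event resumes at the same dose. A repeat non-hematologic event or a third hematologic event ends treatment.

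Two notes to that table bear on the point. Note 2: "DMF can be delayed for a maximum of 14 days; if not restarted in that time-span, study treatment will be permanently discontinued". Note 3: "If dose is decreased for toxicity, dose re-escalation is not planned".

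Section 5.1 defines three dose levels: 120, 240 and 360 mg BID. Its table adds that "all cohorts start at 120 mg PO BID dose for 1 week, then increase to the assigned dose". Level 2, for example, is "120 mg PO BID for 1 week, then escalate to the dose of 240mg PO BID". The Study Summary and section 10.1.1 both mention a possible de-escalation dose, and neither gives it a value. Section 9.1 lists 120 mg as the smallest capsule.

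Sections 5.8 and 6.5 separately allow treatment to stop for unacceptable or unsafe toxicity, or on the judgment of the investigator or treating physician.

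**The concern.** A reduction rule has to give a usable answer at every dose a patient may be taking. This one gives none at 120 mg BID, which is the whole of Level 1 and the first week of Levels 2 and 3.

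It also leaves the starting point of the step undefined: the assigned level, or the dose being taken when the event began. At full dose the two coincide. During the lead-in they differ, and for a Level 3 patient the difference is between stopping and going on to a higher dose after a severe event.

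These patients can fall outside the DLT rules. A Grade 3 non-hematologic event that settles within 7 days does not meet the duration criterion in 5.2, so 5.7 is the main rule that decides what happens next.

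**Working it through.** **Inputs.** Dose levels, lead-in and 56-day treatment: 5.1. Reduction rule and notes: 5.7. Recruitment of 15 to 21 patients: 10.2. Six patients at the selected dose plus three more in expansion: 10.1.1.

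**Step 1: apply the rule to each level and phase** (mg BID).

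| Assigned level and phase | Dose at onset | Step counted from assigned level | Step counted from dose taken |
|---|---|---|---|
| Level 1, all 56 days | 120 | none defined | none defined |
| Level 2, lead-in | 120 | Level 1: stays at 120 | none defined |
| Level 2, full dose | 240 | 120 | 120 |
| Level 3, lead-in | 120 | Level 2: goes on to 240 | none defined |
| Level 3, full dose | 360 | 240 | 240 |

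The full-dose rows work. At Level 1 the rule fails on both readings. Even if 120 mg BID is itself the unnamed de-escalation dose, nothing lies beneath it. The Level 2 lead-in gives an acceptable result on the assigned-level reading. The Level 3 lead-in is the only row in which the dose can rise.

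**Step 2: is the assigned-level reading plausible?** Yes. Section 5.1 uses the term dose level for the numbered Levels 1 to 3, so one level down from Level 3 is naturally Level 2. That regimen reaches 240 mg BID, after a further week at 120 mg BID if the lead-in is repeated.

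**Step 3: does another rule block the rise?** Note 3 applies once a dose has been decreased. Here the dose taken was never decreased, and the rise would be Level 2's own scheduled titration. The Day 8 visit (6.3.2) includes an adverse event assessment, but its written action is to dispense the assigned dose. Sections 5.8 and 6.5 permit stopping without requiring it.

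**Step 4: size of the rise.** 240/120 = 2.0 times the dose at onset. 240/360 = 0.67, so the new target is 33% below the original one.

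**Step 5: planned exposure.** Assume Level 3 is selected (6 + 3 = 9 patients), everyone completes 56 days and no one is replaced. The plan's range is then reproduced as 3 + 3 + 9 = 15 and 6 + 6 + 9 = 21.

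- Total days: 15 × 56 = 840; 21 × 56 = 1,176.
- Level 3 lead-in: 9 × 7 = 63 days; 63/840 = 7.5%; 63/1,176 = 5.4%.
- If Level 3 opens but is not selected: 3 × 7 = 21 to 6 × 7 = 42 lead-in days.
- Level 1, where the instruction cannot be followed but no rise is possible: 3 × 56 = 168 days (168/840 = 20.0%) or 6 × 56 = 336 days (336/1,176 = 28.6%).

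**The case against.** The strongest reply is that Level 1 fails safe: the drug is held, there is no lower level, and note 2 ends treatment after 14 days. No unsafe dose results. That stands, and it makes the Level 1 part a missing instruction rather than a hazard. Staff still have no stated action for a patient who recovers within the 14 days.

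The Level 3 route is also narrow. It depends on one reading. In practice it needs a first non-hematologic event, because a second hematologic event within the lead-in would require event, recovery, restart and recurrence in a single week. The patient must have recovered to Grade 1 or lower, the new target is below 360 mg BID, and a repeat event ends treatment. Section 9.1 says that flushing improves with continued dosing and that gastrointestinal events lessen after the first month, so going on to a reduced target could be defended. All of this limits the harm. If that is the intention, though, the plan should say so; at present the rise follows from an undefined reference point.

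A reader might go further in four ways that the documents do not support:

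- That Level 1 patients can leave treatment only through note 2. Sections 5.8 and 6.5 also allow discretionary stopping.
- That capsule strength rules out any lower dose. It does not exclude 120 mg once daily; the plan simply does not define it.
- That Level 1 days and Level 3 lead-in days can be added into one measure of the problem. The first group fails safe and only the second can be escalated.
- That this gap calls for new replacement or DLT rules. Section 10.3 already replaces a patient with under 7 days of DMF and no DLT. Its 7-day threshold is a separate issue, as is its mismatch with 5.2, which offers replacement only "for a reason that is definitely unrelated to toxicity of the study agent or disease progression". Replacing patients stopped for toxicity could also favour escalation.

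**Conclusion.** The point holds and should be fixed. The restart instruction cannot be carried out at Level 1. For a Level 3 patient with a qualifying lead-in event, a natural reading leads to twice the dose at onset, and no rule clearly forbids it. The documents do not support saying that the plan requires this rise; it is one of two readings.

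The exposed group for a rise is 63 planned patient-days, 5.4% to 7.5% of the total, assuming Level 3 is selected, full 56-day treatment and no replacements. These are days on which a qualifying event could lead to a rise. They are not a probability, because the documents give no rate of Grade 3 or higher events on 120 mg BID. Confidence is high that no lower level is defined. The rise depends on how staff read the rule.

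**What to change.** Change 5.7 only. First, state that a reduction is counted from the dose being taken when the event began. Second, add one row for the events that now trigger a reduction:

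> If the event occurs on 120 mg BID, including the lead-in, the patient must not go above 120 mg BID; because no lower level exists, discontinue study treatment.

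At Level 1 this makes the note 2 outcome explicit. The sponsor could instead name a lower dose; that would close the gap equally well, provided the bar on going above 120 mg BID stays.

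The cost is one definition and one table row, with no new procedures. A few patients would lose further treatment, including Level 2 lead-in patients who could have resumed 120 mg BID on the assigned-level reading. The 5.7 table has no relatedness condition, so the row would also stop patients whose event was unrelated to DMF unless the sponsor adds one.
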